3.1 Introduction and rationale

The increasing shortage of nurses in the Netherlands significantly impacts healthcare capacity¹. Currently, half of all job vacancies in the Netherlands are in healthcare, trade, and business services². Reports indicate that nursing faces the largest labor market shortages among the healthcare professions, with 10,500 vacancies in 2021 and an expected 24,900 by 2031^{3,4}. Enhancing personnel inflow is one of the solutions. In that regard, the Dutch system does not appear to be well-equipped to support the integration of refugees and migrants certified as nurses in their country of origin, into healthcare positions. Recognition of qualifications is characterized by long delays and there is a lack of guidance^{5,6}. In practice, it also takes a considerable amount of time to reach a sufficient level of language proficiency, especially if individuals are unable to work and have limited exposure to the Dutch language. This slows down the speed at which the tests for obtaining a declaration of professional competence, required for Dutch healthcare licensure, are completed. Consequently, many qualified newcomers in healthcare are either underemployed or unemployed⁵. In 2022, the UMCG assessed the interest among nursing newcomer in the Northern region to participate in a fast-track integration programme (Appendix 1). As sufficient interest was confirmed, such a programme was developed that includes a vocational language and intercultural communication course, after which participants begin working as assistant nurses, salaried as care assistants, while receiving guidance toward BIG registration before taking the examinations required for BIG registration (appendix 2). In this process, data were prospectively collected on whether the participating newcomers successfully completed the different phases of the program, the duration of these phases, and the stage of integration and employment situation from which they entered, and consent was obtained from participants to store these data (appendix 3). The programme was initially developed at the UMCG and grew into a multicentre initiative. In collaboration with Healthcare of the North ('Zorg voor het Noorden', ZvhN), a regional network across the three northern provinces, it has expanded to four non-academic hospitals. As this improvement process, which was not initially conceived as a research project, appeared to be successful, it was subsequently decided to analyze the outcomes in a scientific manner. The primary objective is to determine the proportion of participants who are either progressing as planned or successfully completed the program. In addition, a qualitative analysis and a societal business case is conducted to identify where the benefits lie, thereby providing guidance for sustainable implementation once philanthropic funding is phased out. Additionally, the study aims to analyze potential racial microaggression in the workplace.

3.2 Design (including population, method, confounders and outcomes)

In March 2022, the first version of the survey was sent to 22 language schools in the Northern provinces and shared via various social media channels, such as the municipality of Groningen and the Foundation for Refugee Students (UAF). The survey included a digital questionnaire available in 17 languages (appendix 1), designed to collect data on professional background, curriculum vitae, credential evaluation, legal status, years of education and work experience, type of clinical experience, entrustable professional activities, and proficiency in Dutch, and English. The entrustable professional activities offer additional insights beyond traditional diploma evaluation.

Since December 2023, the REDCap recruitment process has been optimized (appendix 4) so that, in addition to skills, competencies are more broadly assessed to gain the best possible insight into the various domains identified by the World Economic Forum (WEF) as the most in-demand skills by organizations⁷. These include cognitive skills, self-efficacy, collaboration, ethics, physical skills, management skills, and technological skills. Based on the submitted

data, potential participants have been identified and invited for an application interview with the core team of the programme. Eligibility criteria include being a refugee or migrant residing in one of the three northern provinces with a nursing background, holding at least a diploma equivalent to the Dutch MBO-4 level, and having practical experience, preferably in a hospital setting. Additionally, candidates were required to demonstrate sufficient learning capacity to participate in a language course at the University of Groningen's Language Centre (LC). An intake at the LC is conducted before or shortly after the application interview to assess the candidate's developmental potential, considering factors such as motivation, initiative, intelligence, and communication skills. Throughout the course of the project, this intake was expanded to include a study skills test (appendix 5), a brief assessment designed to measure the speed at which an individual can learn a language. Candidates have been invited to participate if the LC deems the candidate's learning ability sufficient (based on the intake and, if available, a study skills test), and the application interview is successful.

The primary outcome: the proportion of participants who either progressed as planned, successfully completed the program by obtaining a (conditional) certificate of professional competence, or transitioned to employment as care assistants.

Secondary outcomes include:

- a societal business case and a qualitative analysis to assess the impact of the program on participants and departments
- the influence of competencies on the need for additional guidance
- potential unconscious and conscious racial microaggression in the workplace

Factors considered as potential confounders are:

- sociodemographic characteristics: age, gender, time since arrival in the Netherlands, and family situation
- educational and professional background: level and type of nursing qualification, years of work experience, and previous additional training
- language and cognitive capacity: baseline Dutch and English proficiency, learning capacity as assessed by the study skills test, and motivation and initiative
- programme-related/contextual factors: hospital/department, differences in mentorship/guidance during integration, regional labor market demand, adaptations or optimizations implemented within the program over time

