3.3 Research questions

What is the proportion of participants who progressed as planned or successfully complete the program at 3, 6, and 10 years after start of the programme? What is the societal business case of the programme and what opportunities for improvement can be identified to optimize its sustainability through a qualitative analysis of the impact on both participants and hospital departments? To what extent do competencies across different domains provide insight into when a participant may require additional support? To what extent do conscious or unconscious racial microaggressions occur in the workplace and what opportunities exist to address and mitigate the unconscious form?

4. Study design

4.1 Mono- or multicenter study.	Monocenter study 	Multicenter study 
--	--	--

4.2 Retrospective study or prospective study		Retrospective study 	Prospective study 
4.3 Cross-sectional or follow-up study		Cross-sectional study 	Follow-up study 
4.4 Quantitative or qualitative study		Quantitative study 	Qualitative study 
4.5 Pilot or explorative study?	Not applicable 	Pilot study 	Explorative study 

Explain why it is a pilot or explorative study.

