- Exit position: premature exit, exit as healthcare assistant, exit as BIG-registered nurse (or achievement of a comparable qualification at the paramedical level with a similar background)
- At exit: healthcare assistant or nurse – type of contract and number of hours: 1 Temporary (eg 1 year); 2 Permanent
- Start date as fully qualified nurse (possibly including onboarding period)
- Program underway and on track? program successfully completed; program still in progress and proceeding as planned; dropped out during the medical language program phase; dropped out during the assistant nurse phase due to insufficient background to continue; decided to stop BIG trajectory during assistant nurse phase and continue/start working as a care assistant; Other

For secondary outcomes and other outcomes:

Data to be completed by newcomer

- Years of education completed
- Country of training
- Attempts to have diploma recognized in the Netherlands
- Level achieved according to the diploma evaluation: A level that corresponds in Dutch terms to: diploma from senior secondary vocational education (MBO), qualification level 4, in nursing and care; 2 years of a nominal 4-year bachelor's program in higher professional education (HBO) in nursing; degree of bachelor in higher professional education (HBO) in nursing; degree of master in higher professional education (HBO) in nursing; other level
- Place of work experience: hospital, nursing home or care home, home care, other
- Years of work experience
- Last country you worked in before arriving in the Netherlands?
- Experience in the following types of hospital departments (multiple answers possible)
- Nursing tasks for which you are qualified: measuring blood pressure, wound care, removing stitches/sutures, preparing medication, venous puncture, inserting IV (intravenous) line, inserting urinary catheter, inserting nasogastric tube, resuscitation / CPR (cardiopulmonary resuscitation)
- As a nurse in the hospital, you have day, evening, and night shifts. Each shift lasts 8 hours. What is your attitude towards evening and night shifts? No problem, I am used to working these shifts; It will take some getting used to, but I think I can manage this with my private life; It is difficult to reconcile with my private life
- Years living in the Netherlands at time of entry
- Socioeconomic status at the time of entry

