6.5 Statistical and/or qualitative analysis			
Please specify Statistical Analysis Plan (SAP): a. Description of study population: The study population consists of nursing newcomers who are already enrolled or will enrol in the fast-track integration trajectory at UMCG and participating partner hospitals. This includes both asylum seekers and migrants. Demographic and baseline characteristics include age,			

gender, language proficiency, participant status (asylum seeker or migrant), and socioeconomic and employment background. Participants who provide consent for research purposes will be included in the analysis.

b. Description of preparation of the data for analyses:

Collected data will be pseudonymized and direct identifiers removed. Data cleaning will involve checking for completeness, consistency, and plausibility. Variables will be coded according to pre-specified categories (e.g. employment history, language level). Missing data will be handled using appropriate methods such as multiple imputation or sensitivity analyses, depending on the extent and pattern of missingness. For qualitative data from surveys or interviews, responses will be anonymized and transcribed for coding and thematic analysis.

c. Specify all applicable statistical and/ or qualitative methods. This usually requires an extensive description of the planned analyses and covariates:

Primary outcome analysis: Descriptive statistics and inferential analyses (e.g. proportions, means, standard deviations) will be calculated for successful trajectory completion, BIG registration achievement. Associations with baseline characteristics will be explored using logistic regression or other appropriate multivariable models.

Secondary outcome analysis: Qualitative data from the Regioplan survey will be analyzed using thematic analysis to identify patterns, facilitators, and barriers in the trajectory. Quantitative secondary measures (e.g. language progress, employment outcomes) will be summarized using descriptive statistics and, where appropriate, tested with regression models to explore predictors of success.

Subgroup analyses will consider variables such as asylum seeker vs. migrant status, age groups, gender, and baseline language proficiency.

d. Clarify how this analysis plan, study setup, sample size and design will answer the study questions:

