7.2.2 If consent is asked complete this section		
7.2.2.1 if the potential participant is a patient:		
First contact with potential participant is made by the treatment provider, either by accompanying letter or in person.	Yes 	No 
Informed consent procedure, including signing the IC, will be carried out by the researcher/ research nurse (not the treatment provider).	Yes 	No 
7.2.2.2 For participants that are either patients or non-patients:		

• Recruitment:
 
Potential participants can register via a custom public survey URL: https://redcap.link/trajectnieuwkomers. This link is shared by organizations such as UAF, COA, and municipalities with their clients. Until now, participants who signed up were asked to provide consent for the processing and storage of their personal data for a maximum of four years. In addition, they could consent to the processing and storage of other data they provided for up to six years (after four years anonymized) for research purposes to analyze how well the trajectory fits the participant and to identify areas where newcomers may need additional support (Appendix 4).
 
With the start of this study, participants who register will:
 
 1 Be asked to provide consent for the processing and storage of personal data for up to four years to determine their eligibility for participation in the trajectory. 2 Receive the attached participant information letter and be asked to digitally sign the consent form, granting permission to use their data for research purposes, the analyses as intended within this study. 
Although the 49 participants already enrolled have previously provided consent for the prospective storage of their data, they will be asked again to provide consent for the use of their data for research purposes. This seems justified by the societal and scientific value of these outcomes as analyzing these data may help optimize the trajectory for future participants in other hospitals and improve the chances of successful integration for nursing newcomers. Only the data of participants who provide this additional consent will be used to determine the
		

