- 1 – the knowledge test – includes various elements such as practicing sample questions, completing assignments, attending lessons, becoming familiar with clinical conditions, and gaining understanding of different healthcare sectors, including psychiatry, hospital care, elderly care, home care, and care for individuals with intellectual disabilities.
- 2 – nursing skills – includes, among others, dosage calculations and practice in the skills lab for procedures such as bladder catheterization, injections, feeding tubes, and peripheral IV insertion. As part of component
- 3 – the clinical reasoning interview – participants practice with clinical case studies.

The phases last approximately 4–6, 6–8, and 4–6 months, respectively. Participants are paired with one or two dedicated nurse buddies for onward support and to help set learning objectives. Additional support, such as extra language assistance or coaching by a medical content advisor, is available if needed.

In addition to medical guidance, a key aspect of the programme is the tailored support provided in areas such as municipal contact, registration in the Dutch healthcare system, and, where needed, engagement with other relevant organisations. A project leader with expertise in supporting healthcare newcomers was appointed.

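### The primary proportion counts participants still on plan as successes with no minimum follow-up, so at calendar looks it mixes recency of entry with success and the looks are not comparable

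*Protocol*

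**What the plan says.** Section 3.1 states the primary objective as the proportion of participants "either progressing as planned or successfully completed the program". Section 3.2 gives the primary outcome as "the proportion of participants who either progressed as planned, successfully completed the program by obtaining a (conditional) certificate of professional competence", and adds a third way to count, "or transitioned to employment as care assistants". Section 3.3 asks for the proportion "at 3, 6, and 10 years after start of the programme".

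Section 6.1 collects a status variable in which "program still in progress and proceeding as planned" is a category of its own, apart from completion, the forms of dropout and the move to care-assistant work. It also records the start of the language course, exit dates and certificate dates, and classifies premature exits in windows that reach month 18/24.

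Section 6.5c, under the primary outcome, says descriptive and inferential statistics "will be calculated for successful trajectory completion, BIG registration achievement". It does not mention on-plan status.

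On timing, Appendix 2 gives 3 to 3.5 months for the language course and says of the hospital part: "The phases last approximately 4–6, 6–8, and 4–6 months, respectively". Section 6.3 expects enrolment until March 2031.

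**The concern.** Someone who began the language course last month and someone who holds the certificate carry the same weight in the numerator. The first has had almost no time to drop out. While enrolment continues, any calendar look includes such people, and their share of the denominator falls from look to look. The reported proportion can therefore change when the programme has not.

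The study is descriptive, so this proportion is its main product, and section 4.5 presents the pilot as groundwork for national expansion and policy. If the year-3 figure is partly a count of recent arrivals, it is a poor basis for either. A difference between the three looks could be read as a change in quality when it reflects a change in maturity.

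**Working it through.** **Inputs from the protocol**
- Enrolled so far: 49 (7.2.2). Expected March 2025 to March 2031: 98 in the North and 80 in the Randstad (6.3).
- Trajectory length L: 3 + (4+6+4) = 17 months to 3.5 + (6+8+6) = 23.5 months (Appendix 2).
- Looks at months 36, 72 and 120.

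**Reproducing the plan's enrolment figures.** 49 + 98 + 80 = 227, and 0.7 × 227 = 158.9, given as 159. The rate of 3.3 per hospital per year matches 49/(5 × 3) = 3.27, and 3.27 × 5 × 6 = 98. This supports March 2022, the month of the first survey, as an approximate launch date.

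**Assumptions**
- The looks are calendar looks from March 2022.
- Entry is even within each period: 49 over months 0–36, then 178 over months 36–108, or 178/72 = 2.47 a month.
- Eventual failure q is the same for every entry cohort, and exits are spread evenly over L. The protocol gives no dropout rate, so q is taken from 10% to 40%.
- At first, nobody in progress is behind plan.

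**Share still inside the trajectory at each look**
- Year 3 (N = 49): L/36 = 17/36 to 23.5/36 = 47.2% to 65.3%.
- Year 6 (N = 49 + 89 = 138): 2.47 L/138 = 30.5% to 42.1%.
- Year 10 (N = 227; entry ended 12 months earlier): 2.47 (L − 12)/227 = 5.4% to 12.5%.

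With the 30% lower projection (110 further entrants, 1.53 a month), year 6 becomes 26.0/104 to 35.9/104 = 25% to 35%, and year 10 becomes 7.6/159 to 17.6/159 = 5% to 11%. If early entry ramped up linearly instead, the year-3 share is 1 − ((36 − L)/36)² = 72% to 88%.

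**Excess over the true success proportion.** At years 3 and 6, those inside the trajectory have on average shown half their eventual failures, so the excess is q × share/2. At year 10 they are all 12 months or more in, so it is q × share × (L − 12)/(2L).

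| Eventual failure q | Year 3 | Year 6 | Year 10 |
|---|---|---|---|
| 10% | 2.4–3.3 points | 1.5–2.1 | 0.1–0.3 |
| 20% | 4.7–6.5 | 3.0–4.2 | 0.2–0.6 |
| 40% | 9.4–13.1 | 6.1–8.4 | 0.3–1.2 |

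Example: with true success of 60%, the pooled rule shows 69–73%, 66–68% and 60–61%.

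A second calculation placed dropout in the windows of section 6.1 and took L as 17 to 24 months. For the same 60% it gives 70.6–71.9%, 66.8–67.6% and 60.4–60.9%. Limiting the denominator to people who entered at least L before the look returns the true value at all three looks.

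**Participants behind plan.** Someone in progress but behind plan is not counted as a success. Let b be the share of those in progress who are behind plan. At years 3 and 6 the excess is cancelled when b(1 − q/2) = q/2, so b = q/(2 − q): 0.1/1.9 = 5% for q = 10%, 0.2/1.8 = 11% for q = 20%, and 0.4/1.6 = 25% for q = 40%. Above that the proportion is too low.

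**The case against.** **Direction.** A reader might infer that the rule always inflates success and that a steady programme would always seem to decline. The documents do not support that. The rule credits only people who are on plan, the protocol gives no timetable for being on plan, and section 3.1 itself describes slow recognition and language learning. A modest share behind plan removes or reverses the excess. What stands is that the looks mix maturity with success, whichever way the error falls.

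**Own-start reading.** If the years run from each participant's own start, nearly everyone is past a two-year trajectory and the artefact largely disappears. A reader might go further and say that nobody could then still be on plan at year 3. That is too strong: section 6.1 provides for additional internships, supervised practice and part-time routes, and the Appendix 2 durations are approximate. The calendar reading is still the more natural one, because people who enter up to March 2031 cannot have ten years of their own follow-up by a ten-year programme look.

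**Completion is already covered.** Section 6.5c names completion and registration, and section 6.1 codes each status separately. That makes the repair easy, but it does not change the outcome stated in 3.1, 3.2 and 3.3, and it leaves 3.2 and 6.5c with different endpoints.

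**Regression.** A reader might infer that the planned logistic regression would make features of recent entrants look like predictors of success. The sentence on regression follows completion and registration, so it can be read as modelling those. The inference is not supported.

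**Scale.** The study is a pilot with no power analysis and no planned test across looks. At N = 49, the 95% half-width around 80% is 1.96 × √(0.8 × 0.2/49) = 11 points, more than the 5–7 point excess at q = 20%. That is fair as to size, but sampling error shows in an interval and this error does not.

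**Conclusion.** The point holds, with conditions. As defined, and read at calendar looks, the primary proportion mixes recency of entry with success, and no section sets a minimum follow-up or an entry-cohort denominator. That conclusion rests only on the protocol's trajectory length and continuing enrolment.

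An upward bias needs two further conditions: calendar looks, and few in-progress participants behind plan. It is then mainly a matter of years 3 and 6 and close to nil at year 10. Its size rests on assumed failure rates, even exits and even entry, and cannot be fixed from the documents.

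**What to change.** In 3.1, 3.2, 3.3 and 6.5c:

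1. State the time origin of the 3, 6 and 10 years.
2. Report in progress and on plan as its own row, beside completed, care assistant and dropped out, and give a timetable that defines on plan.
3. Base the primary success proportion on participants with a fixed minimum follow-up from their own start of the language course. Alternatively, use the cumulative incidence of success at a fixed horizon from own start, with exit as a competing event and those still in progress censored at the look.
4. Set the horizon at 24 months or more, long enough for additional internships and part-time routes.
5. Use the same success endpoint in 3.2 and 6.5c.

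No new data are needed; section 6.1 already collects the dates. The cost is precision at the first look, and probably a lower figure there. With even entry, about 49 × 12/36 = 16 people would have 24 months of follow-up at year 3, a 95% half-width of 1.96 × √(0.16/16) = about 20 points around 80%. At year 6 it would be 49 + 12 × 2.47 = about 79 people (9 points), and at year 10, 49 + 60 × 2.47 = about 197 (6 points). The cumulative incidence also uses the partial follow-up of later entrants.
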